5.0 Grouping Factor: None

6.0 Registration Procedures

- 6.1 **To register a patient, access the Mayo Clinic Cancer Center (MCCC) web page and enter the remote registration/ randomization application. The registration/randomization application is available 24 hours a day, 7 days a week. Back up and/or system support contact information is available on the Web site. If unable to access the Web site, call the MCCC Registration Office at [REDACTED] between the hours of 8 a.m. and 5:00 p.m. Central Time (Monday through Friday).**

The instructions for the registration/randomization application are available on the MCCC web page ([REDACTED]) and detail the process for completing and confirming patient registration. Prior to initiation of protocol treatment, this process must be completed in its entirety and a MCCC subject ID number must be available as noted in the instructions.

It is the responsibility of the individual and institution registering the patient to confirm the process has been successfully completed prior to release of the study agent. Patient registration via the registration/randomization application can be confirmed in any of the following ways:

- Contact the MCCC Registration Office ([REDACTED]). If the patient was fully registered, the MCCC Registration Office staff can access the information from the centralized database and confirm the registration.
- Refer to “Instructions for Remote Registration” in section “Finding/Displaying Information about A Registered Subject.”

- 6.2 Correlative Research: A mandatory correlative research component is part of this study, the patient will be automatically registered onto this component (see Sections 3.19d and [14.1](#)).

- 6.3 Documentation of IRB approval must be on file in the Registration Office before an investigator may register any patients.

In addition to submitting initial IRB approval documents, ongoing IRB approval documentation must be on file (no less than annually) at the Registration Office (fax: [REDACTED]). If the necessary documentation is not submitted in advance of attempting patient registration, the registration will not be accepted and the patient may not be enrolled in the protocol until the situation is resolved.

When the study has been permanently closed to patient enrollment, submission of annual IRB approvals to the Registration Office is no longer necessary.

- 6.4 Prior to accepting the registration, registration/randomization application will verify the following:

- IRB approval at the registering institution
- Patient eligibility
- Existence of a signed consent form
- Existence of a signed authorization for use and disclosure of protected health information

- 6.5 Treatment on this protocol must commence at the recruiting institution under the supervision of a hematologist.

- 6.6 Treatment cannot begin prior to registration and must begin ≤ 14 days after registration.
- 6.7 Pretreatment tests/procedures (see Section 4.0) must be completed within the guidelines specified on the test schedule.
- 6.8 All required baseline symptoms (see Section 10.6) must be documented and graded.
- 6.9 Study drug is available on site.

7.0 Protocol Treatment

7.1 Cycle lengths:

Cycles 1-3 = 28 days
 Cycle 4 = up to 56 days
 Cycle 5 = up to 120 days
 Cycles 6-8 = 28 days
 Cycle 9 = up to 56 days
 Cycles 10 and beyond = 28 days

7.2 Treatment Schedule

	Doses and Schedule				
	Agent	Dose Level	Route	Day	Retreatment
Cycles 1-4 Induction (x 4 cycles)	Ixazomib	4 mg	PO	1, 8, 15	Every 28 days
	Pomalidomide	4 mg	PO	Days 1-21	Every 28 days
	Dexamethasone	40 mg	PO	1, 8, 15, 22	Every 28 days
Cycle 5 Transplantation ^{a,e,f}	Stem cell mobilization ^b followed by single ASCT				
Cycles 6-9 Consolidation ^c (x 4 cycles)	Ixazomib	4 mg	PO	1, 8, 15	Every 28 days
	Pomalidomide	2 mg	PO	Days 1-21	Every 28 days
	Dexamethasone	40 mg	PO	1, 8, 15, 22	Every 28 days
Cycles 10 and Beyond Maintenance (until progression or unacceptable toxicity) ^d	Ixazomib	4 mg	PO	1, 8, 15	Every 28 days

- SCT:** Can be performed per institutional practice. Stem cells collected and cryopreserved ahead of time or collected immediately prior to transplant can be used. Conditioning regimen preference left to the treating physician, but should not be enrolled in any additional therapy trials.
- If not previously collected and cryopreserved.
- If a patient previously has a dose reduction in induction, the consolidation phase will start and continue at reduced dose.
- Ixazomib maintenance would start at 4 mg unless dose has been previously reduced in the Induction or consolidation phase due to a non-hematologic toxicity specifically attributed to Ixazomib.
- Window period is 2-4 weeks between Induction and ASCT; 60-120 days between ASCT and Consolidation and 0-4 weeks between the Consolidation and Maintenance phases.
- Melphalan conditioning followed by stem cell infusion is being considered as 'cycle 5' for logistical reasons only. No additional toxicity data will be collected in the immediate post ASCT period until day 60-100 when the patient returns for routine post ASCT-reevaluation.

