8.0 Dosage Modification Based on Adverse Events

Strictly follow the modifications in this table for the first **two** cycles, until individual treatment tolerance can be ascertained. Individual drugs can be dose reduced as per the table below depending on the adverse event attribution. Thereafter, these modifications should be regarded as guidelines to produce mild-to-moderate, but not debilitating, side effects. If multiple adverse events are seen, administer dose based on greatest reduction required for any single adverse event observed. Reductions apply to treatment given in the preceding cycle and are based on adverse events observed since the prior dose.

NOTE: If either of pomalidomide or ixazomib is discontinued, the patient can continue on the other drugs, unless specified otherwise in the dose modification tables. If both are discontinued, the patient will go to event monitoring (Section 18.0).

ALERT: *ADR reporting may be required for some adverse events (See Section 10)8.1*

Dose Levels for each drug in the combination

(Based on Adverse Events in Tables 8.2-4)

NOTE: One drug can be reduced each time based on the drug most likely related to the toxicity observed.

Ixazomib (Days 1, 8, 15)		Pomalidomide (Day 1-21)		Dexamethasone (Days 1, 8, 15, 22)	
Starting dose	4 mg	Starting dose	4 mg	Starting dose	40 mg
-1	3 mg	-1	3 mg	-1	20 mg
-2	2.3 mg	-2	2 mg	-2	12 mg
-3	2.3 mg Days 1, 15	-3	1 mg	-3	4 mg
-4	Discontinue	-4	Discontinue	-4	Discontinue

If patients cannot tolerate dose level –3 of ixazomib AND pomalidomide they will go to event monitoring per Section 4.2. If dexamethasone is discontinued, the patient may continue treatment.

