8.3 Dose modifications for pomalidomide based on adverse events during a cycle

(For each cycle during induction and consolidation and maintenance)

Table 8.3			
CTCAE System/Organ/Class (SOC)	ADVERSE EVENT	AGENT	ACTION**
Investigations	Neutrophil count decreased If ANC $<1.0 \times 10^9/L$ or ANC $>1.0 \times 10^9/L$ (up to LLN) with fever (temperature $>38.5^\circ C$)	Pomalidomide	Omit pomalidomide dose. Follow CBC weekly. If neutropenia has resolved to \leq Grade 2 prior to Day 21 and fever has resolved, restart pomalidomide at next lower dose level and continue through Day 21 of a 28-day cycle. If febrile neutropenia is the only toxicity for which a dose reduction is required, G-CSF may be used and the pomalidomide dose maintained.
Investigations	Platelet count decreased If platelet count $<30 \times 10^9/L$	Pomalidomide	Omit pomalidomide dose Follow CBC weekly Hold anticoagulation/antiplatelet therapy until platelets $\geq 50,000/mm^3$ If platelet count resolves to \leq Grade 2 prior to Day 21, restart pomalidomide at next lower dose level and continue through Day 21 of each cycle
Skin and subcutaneous tissue disorders	Rash maculopapular Grade 2 or 3	Pomalidomide	Omit pomalidomide dose; follow weekly If the AE resolves to \leq Grade 1 prior to Day 21, restart pomalidomide at next lower dose level and continue through Day 21 of each cycle
	Grade 3-4 Stevens –Johnson Syndrome	Pomalidomide	Discontinue pomalidomide and remove patient from all study treatment
	\geq Grade 3 Erythema multiforme	Pomalidomide	Discontinue pomalidomide and remove patient from all study treatment

Table 8.3			
CTCAE System/Organ/Class (SOC)	ADVERSE EVENT	AGENT	ACTION**
	Erythroderma ≤Grade 3	Pomalidomide	Omit pomalidomide dose; follow weekly If the AE resolves to ≤Grade 1 prior to Day 21, restart pomalidomide at next lower dose level and continue through Day 21 of the 28-day cycle
	Rash, maculo-papular Rash, acneiform Grade 4	Pomalidomide	Discontinue pomalidomide and remove patient from all study treatment
Nervous system disorders	Peripheral sensory neuropathy Grade 3	Pomalidomide	Omit pomalidomide dose and follow at least weekly. If the AE resolves to ≤Grade 1 prior to Day 21, restart pomalidomide at next lower dose level and continue through Day 21 of the 28-day cycle
	Peripheral sensory neuropathy Grade 4	Pomalidomide	Discontinue pomalidomide and remove patient from all study treatment

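### Footnote c of Section 7.2 puts no 2 mg ceiling on consolidation pomalidomide after an induction reduction, and Tables 8.2 and 8.3 set different restart grades for the same Grade 3 event

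*Combined protocol and SAP*

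**What the plan says.** **Dose carried into consolidation.** In Section 7.2 the induction row (cycles 1-4) gives pomalidomide 4 mg on Days 1-21. The consolidation row (cycles 6-9) gives "Pomalidomide 2 mg PO Days 1-21". Ixazomib (4 mg) and dexamethasone (40 mg) are the same in both phases. Footnote c, attached to the consolidation row, reads: "If a patient previously has a dose reduction in induction, the consolidation phase will start and continue at reduced dose". Footnote d, on maintenance, is more specific, naming both its drug and its starting dose: "Ixazomib maintenance would start at 4 mg unless dose has been previously reduced in the Induction or consolidation phase".

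Table 8.1 has one ladder per drug. Its starting row, in the order ixazomib, pomalidomide, dexamethasone, is "Starting dose 4 mg Starting dose 4 mg Starting dose 40 mg". The pomalidomide steps below that are 3, 2 and 1 mg, then discontinuation. There is no separate consolidation ladder, and Table 8.3 is headed "For each cycle during induction and consolidation and maintenance".

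**Restart after a Grade 3 event.** Table 8.2 is titled for ixazomib, but its row for other non-hematologic Grade 3 events names pomalidomide in both the agent and action columns. That row requires resolution to Grade 1 or lower, or baseline, before restart one level down. As the list can be read in this text, the row excepts Grade 3 fatigue, nausea or emesis without optimal anti-emetic prophylaxis, and diarrhea without optimal supportive therapy. Table 8.3, in its row for other non-hematologic events of Grade 3 or above, lets pomalidomide restart one level down once the toxicity is Grade 2 or lower before Day 21.

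**Force of the tables.** Section 8.0 says "Strictly follow the modifications in this table for the first" two cycles, and then: "Thereafter, these modifications should be regarded as guidelines to produce mild-to-moderate, but not debilitating, side effects".

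**The concern.** Footnote c is meant to protect patients who have already needed a reduction. Because the scheduled pomalidomide dose itself falls between phases, carrying the reduced dose forward can do the opposite: a patient who could not tolerate 4 mg is scheduled for more pomalidomide after transplant than one who could. The footnote sits in Section 7.2 and applies from cycle 6, so the relaxation of the Section 8 tables after cycle 2 does not clearly reach it.

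On restart, the two tables give opposite instructions for the same drug and event. If a Grade 3 event has improved to Grade 2 and baseline was lower, one table holds pomalidomide and the other restarts it. The conflict matters most in the first two cycles, when both tables are to be followed strictly. At stake in both parts is dosing safety in patients who have already shown toxicity.

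**Working it through.** No figure stated in the plan is in dispute. As a side check, the decision rule (at least 14 successes in 21) reproduces: P(X ≥ 14) is 0.0946 at a true rate of 0.50 (stated 0.095) and 0.8701 at 0.75 (stated 0.870). Neither depends on the dosing text.

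**Part 1: footnote c applied to the Table 8.1 ladder.** Inputs are the ladder of 4, 3, 2 and 1 mg (Table 8.1), scheduled consolidation of 2 mg, and 21 dosing days per cycle over four cycles (Section 7.2). Amount per cycle = daily dose × 21.

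| Status at end of induction | Carry the reduced dose forward | Lower of induction dose and 2 mg |
|---|---|---|
| Never reduced (4 mg) | footnote c not triggered: 2 mg, 42 mg/cycle | min(4, 2) = 2 mg, 42 mg/cycle |
| Level -1 (3 mg) | 3 mg, 63 mg/cycle | min(3, 2) = 2 mg, 42 mg/cycle |
| Level -2 (2 mg) | 2 mg, 42 mg/cycle | min(2, 2) = 2 mg, 42 mg/cycle |
| Level -3 (1 mg) | 1 mg, 21 mg/cycle | min(1, 2) = 1 mg, 21 mg/cycle |

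The readings differ only at level -1. The excess there over a never-reduced patient is 63 − 42 = 21 mg per cycle (63/42 = 1.5). Over four full cycles it is 4 × 63 − 4 × 42 = 252 − 168 = 84 mg. For ixazomib and dexamethasone the scheduled dose is the same in both phases, so carrying a reduction forward cannot exceed the schedule.

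**Part 2: the two restart rules side by side.** Take an other non-hematologic Grade 3 event attributed to pomalidomide, outside the Table 8.2 exceptions, with baseline Grade 0 or 1.

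| Grade reached before Day 21 | Table 8.2 | Table 8.3 |
|---|---|---|
| Still 3 | hold | hold |
| 2 | hold | restart one level lower |
| 1 or lower | restart one level lower | restart one level lower |

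The tables part only while the event stands at Grade 2. With k dosing days at Grade 2 and a first reduction to 3 mg, the difference is k × 3 mg. The documents do not give k. Assuming one day it is 3 mg, one week 7 × 3 = 21 mg, and two weeks 14 × 3 = 42 mg.

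Three places might settle the conflict, and none does. Section 8.11 requires Grade 1 or lower, or baseline severity, but only for starting a new cycle. The greatest-reduction rule in Section 8.0 concerns dose size when several events occur, not the grade for restart. The title of Table 8.2 points to ixazomib, but the row itself directs pomalidomide dosing.

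The rest of Table 8.3 shows which threshold is the outlier. Every other non-hematologic row that sets a restart grade (maculopapular rash, erythroderma, sensory neuropathy, allergic reaction) uses Grade 1 or lower. Grade 2 otherwise appears only in the neutrophil and platelet rows.

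**The case against.** The best defence of footnote c is its position. It annotates a row scheduled at 2 mg and is plainly meant to restrict dosing, so using it to exceed that row defeats its purpose. This is persuasive on intent: 2 mg is the likely meaning. It does not remove the problem, because no text states 2 mg as a ceiling. Section 8.11 also carries a reduced dose level forward between cycles, which makes the 3 mg reading easy to reach. It is also fair that 3 mg is below the 4 mg induction dose (63 against 4 × 21 = 84 mg per cycle) and that Table 8.3 still governs toxicity during consolidation.

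On restart, a reader has some basis for preferring the pomalidomide table for pomalidomide. Section 8.11 limits the difference to the remaining Days 1-21 of one cycle, and after cycle 2 the tables are only guidelines. All of this narrows the point. In cycles 1-2, however, two rules to be followed strictly still cannot both be obeyed.

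Two stronger readings are tempting. A reader might infer that the protocol prescribes 3 mg for these patients; it does not, it merely fails to exclude it. A reader might also infer a threefold spread by adding a third meaning, one level below the scheduled 2 mg, giving 1 mg or 21 mg per cycle. Nothing in the documents supports stepping down again from the already halved dose, so the supported spread is 1.5-fold.

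**Conclusion.** Both parts hold as a minor dose-safety correction. Footnote c lacks a ceiling. If it is read as carry-forward, a patient at exactly level -1 starts consolidation at 3 mg against the scheduled 2 mg, an excess of 21 mg per cycle and at most 84 mg over four full cycles. The in-cycle restart threshold for pomalidomide is contradictory between Tables 8.2 and 8.3 for Grade 3 non-hematologic events outside the Table 8.2 exceptions. The cost there is one dose per dosing day spent at Grade 2.

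The exception list is taken as covering the gastrointestinal and fatigue entries that follow it, since the table is broken across rows. The comparison is for events attributed to pomalidomide; events attributable to either drug carry a further instruction in both tables. How many patients either part would touch cannot be derived from the documents and may be zero. Nothing here supports inferring that the 18-month progression-free survival assessment is compromised: endpoint, 21 evaluable patients, alpha of 0.095 and power of 0.870 stand as stated.

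**What to change.** **Footnote c.** Replace with: *Consolidation pomalidomide starts at the lower of the last tolerated induction dose and 2 mg; ixazomib and dexamethasone continue at any reduced induction dose; a drug permanently discontinued in induction is not restarted.* This gives 2, 2, 2 and 1 mg for never reduced and levels -1, -2 and -3. The last clause is needed because Section 8.0 lets a patient who stops pomalidomide continue on the other drugs. Without it, someone who stopped at 4 mg could be read as restarting at 2 mg.

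**Table 8.3, other non-hematologic row.** For Grade 3 events outside the Table 8.2 exceptions, set the restart threshold to Grade 1 or lower, or baseline. Refer Grade 4 events to the Table 8.2 Grade 4 row, which asks for permanent discontinuation to be considered. Restating the exceptions matters. A row-wide change would also catch Grade 3 fatigue, and fatigue was the most common Grade 3/4 non-hematologic toxicity (17%) in the pomalidomide-dexamethasone phase II study described in Section 1.5.

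**Cost.** One footnote and one table row by amendment. The downside is small: some pomalidomide doses are omitted for longer, one per dosing day at Grade 2. No change to sample size, alpha or power.

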8.11 Instruction for initiation of a new cycle of therapy

A new cycle of treatment may begin on the scheduled Day 1 of a new cycle if:

- The ANC is $\geq 1.0 \times 10^9/L$ (=1000/microliter)
- The platelet count is $\geq 75 \times 10^9/L$ unless the participant has $\geq 50\%$ bone marrow infiltration in which case a platelet count of $\geq 50 \times 10^9/L$ is allowed
- Any other non-hematologic treatment -related adverse event that may have occurred has resolved to \leq Grade 1 or baseline severity.

If these conditions are not met on Day 1 of a new cycle, the subject will be evaluated weekly and a new cycle of therapy will be held until the toxicity has resolved as described below

If any drug dosing was halted during the previous cycle and was restarted with a one-level dose reduction without requiring an interruption for the remainder of the cycle, then that reduced dose level will be initiated on Day 1 of the new cycle.

If any drug dosing was omitted for the remainder of the previous cycle or if the new cycle is held due to known hematologic toxicity newly encountered on the scheduled Day 1, then the new cycle will be started with a one-level dose reduction. If a new cycle of therapy cannot be restarted within 4 weeks of the scheduled Day 1 due to non-resolution of drug related toxicities, the patient will be removed from protocol therapy and will go to event monitoring.

→ → Use the NCI Common Terminology Criteria for Adverse Events (CTCAE) version 4.0* unless otherwise specified ← ←

8.2 Dose modifications for ixazomib based on adverse events during a cycle (for each cycle during induction and consolidation and maintenance)

CTCAE System/Organ/Class (SOC)	ADVERSE EVENT	AGENT[#]	ACTION^{**}
Blood and lymphatic system disorders	Febrile neutropenia If platelet count $<30 \times 10^9/L$ or ANC $<1.0 \times 10^9/L$ or ANC $>1.0 \times 10^9/L$ (up to LLN) with fever (temperature $>38.5^\circ C$)	Ixazomib	Days 2-15: Ixazomib dose should be omitted. Complete blood count (CBC) with differential should be followed weekly. If ANC is $\geq 1.0 \times 10^9/L$ and/or platelet counts $\geq 30 \times 10^9/L$, ixazomib may be reinitiated with 1 dose level reduction (see Table 8.1). The subsequent cycle will use the reduced dose
Nervous System Disorders	Peripheral motor neuropathy OR Peripheral sensory neuropathy Newly developed Grade 1 with pain or \geq Grade 2	Ixazomib	Reduce dose of ixazomib to the next lower dose level

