- Hold/Delay = The current dose(s) of all drugs during a cycle is delayed. The patient does make up the delayed dose(s) when the patient meets the protocol criteria to restart drugs.
- Discontinue = The specified drug(s) are totally stopped.

NOTE: For adverse events attributable to both ixazomib and pomalidomide, only one of the drugs should be reduced for each incidence of AEs severe enough to necessitate dose reduction. The drug reduced should alternate starting with pomalidomide for the first dose reduction.

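### Read literally, footnote c to Section 7.2 starts consolidation at pomalidomide 3 mg for a patient reduced once in induction, above the 2 mg scheduled for a patient never reduced

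*Combined protocol and SAP*

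**What the plan says.** The Section 7.2 table gives the induction dose (Cycles 1-4) as "Pomalidomide 4 mg PO Days 1-21 Every 28 days" and the dose under "Cycles 6-9 Consolidation" as "Pomalidomide 2 mg PO Days 1-21 Every 28 days". Ixazomib (4 mg) and dexamethasone (40 mg) have the same scheduled dose in both phases. Pomalidomide is the only drug whose scheduled dose changes.

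Footnote c, attached to the consolidation row, reads: "If a patient previously has a dose reduction in induction, the consolidation phase will start and continue at reduced dose". It does not say which drug it covers or which dose the reduction is measured from. Footnote d, on maintenance, is more careful: it names ixazomib, gives a starting dose, and says what kind of earlier toxicity counts.

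The table in Section 8.1, "Dose Levels for each drug in the combination", has one starting row: "Starting dose 4 mg Starting dose 4 mg Starting dose 40 mg" (ixazomib, pomalidomide and dexamethasone in that order). Pomalidomide then steps to 3, 2 and 1 mg before discontinuation. No second ladder starts from 2 mg, and the heading of Section 8.3 applies the same pomalidomide rules to all three drug-treatment phases.

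**The concern.** A carry-over rule for dose reductions should never give a patient with earlier toxicity more drug than a patient without it. Footnote c does this at one point on the ladder, because the scheduled pomalidomide dose drops by two levels between phases while the footnote carries forward the level reached in induction.

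That point is easy to reach. Level -1 is where a first step down from 4 mg lands. For toxicity attributed to both pomalidomide and ixazomib, the note closing Section 8.2 says: "The drug reduced should alternate starting with pomalidomide for the first dose reduction". The first such event takes pomalidomide to 3 mg and the second reduces ixazomib, so pomalidomide is still at 3 mg after two events.

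Patient safety and consistent dosing after transplant are at stake. The primary analysis is not affected.

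**Working it through.** **Inputs**
- Scheduled pomalidomide: 4 mg in induction and 2 mg in consolidation, 21 days per cycle, four consolidation cycles (Section 7.2).
- Ladder: 4, 3, 2, 1 mg (Section 8.1).
- Carry-over rule: footnote c, read literally as the dose reached by the end of induction.

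**Formula.** Dose per cycle = daily dose × 21 days. Ratio = literal dose ÷ scheduled dose.

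| End of induction | Literal consolidation dose | Per cycle | Scheduled per cycle | Ratio |
|---|---|---|---|---|
| Never reduced (4 mg) | 2 mg | 2 × 21 = 42 mg | 42 mg | 1.00 |
| Level -1 (3 mg) | 3 mg | 3 × 21 = 63 mg | 42 mg | 63/42 = 1.50 |
| Level -2 (2 mg) | 2 mg | 2 × 21 = 42 mg | 42 mg | 1.00 |
| Level -3 (1 mg) | 1 mg | 1 × 21 = 21 mg | 42 mg | 21/42 = 0.50 |

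Over four cycles with no omission or further reduction, level -1 gives 4 × 63 = 252 mg against 4 × 42 = 168 mg, a difference of 84 mg.

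**Does another section cap the dose?** Section 8.11 is the only other rule on carrying a reduced dose into a new cycle. Its carry-forward clause opens "If any drug dosing was halted during the previous cycle". Before Cycle 6 the previous cycle is Cycle 5, the transplant, in which pomalidomide is not scheduled. The clause therefore does not set the Cycle 6 dose, and it contains no ceiling. No other section supplies one.

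**How many patients?** The documents do not give the proportion expected to end induction at level -1. Section 1.5 reports grade 3 or 4 neutropenia in 21 of 60 patients (35%) on pomalidomide 2 mg daily with dexamethasone, all first seen in Cycles 1-3. That regimen differs from this one, and neutropenia is not the same as ending at level -1. Purely as an assumption, 10% to 35% of the 21 evaluable patients would be 0.10 × 21 = 2.1 to 0.35 × 21 = 7.35, or about 2 to 7.

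**Effect on the design.** The decision rule is at least 14 successes in 21 patients. The exact binomial probability of 14 or more is 0.0946 at a true rate of 0.50 and 0.8701 at 0.75. These match the 0.095 and 0.870 in Section 16.24, and the footnote does not enter either calculation.

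**The case against.** The strongest reply is that 3 mg is not a natural reading of a reduced dose in a phase scheduled at 2 mg. On this view the footnote is ambiguous rather than wrong. It could mean 3 mg (the carried-over dose), 2 mg (the lower of the two) or 1 mg (one level below the consolidation dose), and 3 mg is the least likely intent. The point about intent stands. It does not remove the problem: the footnote says consolidation starts and continues at the reduced dose after a reduction in induction, and the only reduced dose such a patient has is the 3 mg on the ladder. If all three readings are allowed, the same patient could receive 21, 42 or 63 mg per cycle depending on who reads the footnote.

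Second, the affected group is narrower than all patients with pomalidomide toxicity. For other severe non-hematologic events attributable to either drug, Sections 8.2 and 8.3 call for pomalidomide to be discontinued first. Febrile neutropenia alone may be managed with G-CSF at an unchanged dose, and thromboembolic events keep the dose level. This is correct and limits the numbers. It does not change where a reduction lands when one is made.

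Third, Section 8.0 treats its modifications as guidance after the first two cycles, and Section 8.11 requires recovery of counts and toxicity before a cycle starts. The first provision covers the adverse-event modifications, not footnote c in Section 7.2. The second governs when a cycle may begin, not the carried-over dose.

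Finally, the risk is bounded. The patient has already taken 3 mg, blood counts are scheduled in consolidation (Days 8, 15 and 22 of Cycles 6-8 and Day 15 of Cycle 9), and the rules for omitting and reducing doses remain. That stands and limits the severity.

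**Conclusion.** The concern holds. Followed literally, footnote c gives a patient who ended induction at level -1 50% more pomalidomide per consolidation cycle than a patient who tolerated 4 mg throughout. The excess is 21 mg per cycle (63 − 42), or 84 mg over four unmodified cycles. It occurs at level -1 only and for pomalidomide only.

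The conclusion rests on reading the reduced dose as the dose reached in induction and on there being no ceiling elsewhere in the protocol. The count of affected patients is unknown. This should be corrected because it is a written dosing instruction that runs the wrong way after toxicity. It does not threaten the trial's statistical conclusions.

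**What to change.** Replace footnote c with:

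> A reduction of ixazomib or dexamethasone made in induction carries over unchanged into consolidation. For pomalidomide, consolidation starts at the lower of 2 mg and the final induction dose, and any later reduction moves down Table 8.1 from that dose.

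Final induction doses of 4, 3, 2 and 1 mg then give consolidation starting doses of 2, 2, 2 and 1 mg, and the inversion disappears. Patients at levels -1 and -2 would receive the same dose as patients never reduced. If the sponsor wants a further step down for them, the footnote should state that dose instead.

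The cost is one footnote sentence in a protocol amendment, with no extra patients, tests or data.
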